5.1.2. Design Overview

- A screening phase of up to 6 weeks in duration
- 52-week open-label study drug treatment phase with standardized prednisone taper
- A 12-week follow-up phase to ensure that all subjects are evaluated for safety at 12 weeks after receiving the last dose of study drug.

5.2. Study Design and Methods

This open-label, single-center pilot study will enroll and treat 15 subjects with relapsing GCA. All subjects will receive oral baricitinib 4 mg daily for a duration of 12 months. All patients with GCA enrolled will have undergone a recent relapse within 6 weeks prior to study entry. In response to the observed relapse, prednisone will be re-instituted (for patients who have previously tapered off glucocorticoids) or increased (for patients currently on glucocorticoids) based on the level of glucocorticoid treatment the patient was on when the relapse occurred, as further outlined below.

Subjects with evidence of relapse will be recruited from the clinical practice of Mayo Clinic Rheumatology. If initial inclusion criteria are met, the subject will be consented and begin screening for study enrollment. The screening period may be as short as 2 weeks or as long as 6 weeks. During the screening period, treating physicians may increase prednisone in the following manner: if relapse occurred with prednisone doses ≥ 20 but <30 mg/day, an increase to at least 30 mg/day (but not to exceed 40 mg/day) will occur. For those with relapse present with prednisone dose ≥ 10 but <20 mg/day an increase to at least 20 mg/day (but not to exceed 30 mg/day) will occur. For those with relapse occurring with prednisone from 0 to <10 mg/day, a reinstatement or increase to at least 10 mg/day (but not exceeding 20 mg) will occur. This increase will occur during the screening phase following informed consent. The prednisone increase is in response to the observed relapse, in keeping with standard clinical practice.

To be enrolled, subjects must have clinically stable disease and treated with a prednisone dose of either 30 mg, 20 mg, or 10 mg (in accordance with their respective entry tier) for a minimum of 2 weeks before initiation of study drug and standardized taper. As such, the patient is not, by the physician's clinical assessment, showing signs of worsening disease (new symptoms or increasing severity of the symptoms that were observed at time of relapse) attributable to GCA. For example, a patient with relapse occurring at 30 mg prednisone may be increased to 40 mg/day for 2 weeks, 35 mg/day for 2 weeks and then 30 mg/day for two weeks. If deemed clinically stable on 30 mg/day prednisone after two weeks, the subject may enroll and begin study drug and standardized glucocorticoid taper. Additional examples: 1) if a relapse occurred at 15 mg/day, a patient may be increased to 20 mg for 2 weeks and if deemed clinically stable may undergo initiation of study drug after being on 20 mg for 2 weeks; 2) if a patient has previously been able to discontinue prednisone therapy and has a clinical relapse, prednisone can be re-initiated at 10 mg/day and if clinically stable at 2 weeks may proceed to enrollment. Once enrolled, subjects will begin study drug and reduce their prednisone dose on a standardized tapering schedule according to their respective entry dose (30 mg, 20 mg, 10 mg), as outlined in **Table 1**.

If a relapse occurs during the standardized taper (without evidence of severe ischemic event: defined as stroke, vision loss, critical limb ischemia) the patient will be removed from the standardized prednisone taper regimen but continue study drug for the remaining balance of the 52-week study period, provided no contraindication or criteria for study drug withdrawal is present at time of relapse. Once removed from the standardized prednisone taper, subsequent prednisone dose and management will be at the discretion of the treating provider. If a second relapse occurs, or if a relapse with the accompaniment of an aforementioned severe ischemic event is observed, then the study drug will be discontinued and prednisone and/or other alternative treatments will be provided as directed and at the discretion of the treating provider.

Safety and efficacy data will be collected at the time of each clinical visit. In the absence of disease worsening, relapse, or drug toxicity, subjects will continue baricitinib for 52 weeks. Following completion of 52 weeks of treatment, all subjects will discontinue baricitinib. For safety purposes a follow-up visit will occur 12 weeks after discontinuation of the study drug for all

subjects, including those with earlier study drug withdrawal.

The maximum duration of subject participation (including screening) is 70 weeks. Completion of the study is defined as completion of the 52-week treatment period and 12-week follow-up visit.

TABLE 1: Standardized prednisone taper

Time (Week)	Prednisone dose and tapering schedule		
Screening: -6 to -2*	30	20	10
0	30	20	10
1	25	17.5	9
2	22.5	15	8
3	20	12.5	7
4	17.5	10	6
5	15	9	5
6	12.5	8	5
7	10	7	4
8	9	6	4
9	8	5	3
10	7	5	3
11	6	4	2
12	5	4	2
13	5	3	1
14	4	3	1
15	4	2	0
16	3	2	
17	3	1	
18	2	1	
19	2	0	
20	1		
21	1		
22	0		

*subjects must be on stable dose of either 30 mg, 20 mg, or 10 mg for 2 weeks prior to baseline (week 0)

5.3. Treatment Arms and Duration

This is an open-label, single-arm study. All subjects will receive the study drug for a maximum of 52 weeks in combination with a standardized prednisone taper.

5.4. Type and Number of Subjects

The study population will be comprised of 15 subjects with GCA who have experienced a relapse, determined by demonstrating active disease, within 6 weeks of baseline. Active disease will be defined as showing evidence of signs or symptoms attributable to GCA and the presence of either an ESR \geq 30 mm/hr or a CRP \geq 10 mg/L. Subjects demonstrating symptoms of visual manifestations (i.e. double vision, transient or permanent partial/complete vision loss), cerebrovascular compromise (ischemic stroke deemed secondary to GCA), or limb ischemia will be ineligible for enrollment. Patients on glucocorticoids for \geq 4 years consecutively (without interruption of more than 1 month) will be excluded to avoid issues with precipitating secondary adrenal insufficiency and/or symptoms of steroid withdrawal from an accelerated standardized glucocorticoid taper.

5.5. Design Justification

This is a single-center, open-label study to evaluate the safety of baricitinib in GCA and to develop preliminary evidence of efficacy to support the potential conduct of a larger randomized trial.

The design of this study is similar in to other open-label phase II studies evaluating biologic medications in subjects with GCA [29, 38].

Glucocorticoids represent the only current standard of care treatment for patients with GCA. As such, prednisone will be continued during the initiation of the study drug. Subjects will enter the study at one of three doses of prednisone (30 mg, 20 mg, or 10 mg). Subjects should be on a stable prednisone dose for a minimum of 2 weeks (maximum 6 weeks) prior to initiation of study drug. Following study drug initiation prednisone tapering will occur in a standardized manner.

The 52-week study duration was chosen to assess for safety of medication use as well as to observe preliminary evidence of efficacy based on duration of glucocorticoid-free remission and relapse-free survival.

5.6 Dose Justification

5.6.1. Baricitinib

Subjects will receive a fixed dose of baricitinib, 4 mg oral daily, for duration of 52 weeks. The dose of baricitinib will remain constant throughout the study. If serious adverse events occur related to the study medication, the dose will not be decreased rather the study drug will be withdrawn.

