6.2. Risk Assessment

There are currently no known contraindications or identified risks requiring special warnings or special precautions for use of Baricitinib. Potential risks have been identified and are detailed in the included accompanying Investigator Brochure for Baricitinib (LY3009104). Potential risks are summarized below.

Increased Adverse Events Due to Increased Exposures in Patients with Renal Impairment:

Data from completed studies indicate that subjects with renal impairment have increased exposure to baricitinib. Increased exposure could place a person at increased risk for any other risk that is related to exposure. Investigators will follow dosing guidelines specified in the protocol, and monitor creatinine in study subjects and follow protocol drug interruption and discontinuation criteria.

Myelosuppression: Baricitinib is anticipated to down-regulate the JAK pathway and result in changes to white blood cell counts. Although dose-related decreases in neutrophils and other phagocytic cell lines have been observed, neutropenia and lymphocytopenia have been observed infrequently. Investigators will monitor leukocyte parameters in study subjects and follow protocol drug interruption and discontinuation criteria.

Increased Infections (including opportunistic infections and herpes zoster): In addition to the observed decreases in phagocytic cells, JAK inhibition down-regulates cytokines related to the immune system. Although infections and infestations were the most frequently reported treatment emergent adverse event (TEAE) occurrence of infections typically considered to be opportunistic has not been observed in clinical studies with baricitinib. The incidence rate of herpes zoster observed in baricitinib studies is within the range reported in observational studies and clinical trials of patients with RA. Investigators will monitor subjects for clinical signs and symptoms of infectious events, including herpes zoster. If a subject is clinically diagnosed with herpes zoster, the investigator will interrupt investigational product, initiate standard of care

(including antiviral therapy and relevant supportive care as appropriate), monitor for multi-dermatomal involvement or other evidence of dissemination, and follow subjects until clinical recovery of skin lesions (vesicles).

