10. WITHDRAWAL/STOPPING CRITERIA

10.1. Interruption of Investigational Product

In some circumstances, it may be necessary to temporarily interrupt treatment as a result of an adverse event (AEs) or abnormal laboratory values that may have an unclear relationship to investigational product. Retest timing and frequency is at the investigator's discretion.

Investigational product must be held in the following situations and may be resumed as noted in the **TABLE 3**.

Table 3. Criteria for Temporary Interruption of Investigational Product

Hold investigational product if the following laboratory test results occur:	Investigational product may be resumed when:
WBC count <2000 cells/ μ L	WBC count \geq 2500 cells/ μ L
ANC <1000 cells/ μ L	ANC \geq 1200 cells/ μ L
Lymphocyte count <500 cells/ μ L	Lymphocyte count \geq 750 cells/ μ L
Platelet count <75,000/ μ L	Platelet count \geq 100,000/ μ L
eGFR <40 mL/min/1.73 m ² (from serum creatinine)	eGFR \geq 50 mL/min/1.73 m ²
ALT* or AST >5 x ULN	ALT and AST return to <2 x ULN, and investigational product is not considered to be the cause of enzyme elevation
Hemoglobin <8 g/dL	Hemoglobin \geq 10 g/dL
Symptomatic herpes zoster	All skin lesions have crusted and are resolving
Severe infection that, in the opinion of the investigator, merits the IP being discontinued	Resolution of infection
Abbreviations: ALT = alanine aminotransferase; ANC = absolute neutrophil count; AST = aspartate aminotransferase; eGFR = estimated glomerular filtration rate; IP = investigational product; ULN = upper limit of normal; WBC = white blood cell. *ALT will be used for monitoring purposes. If abnormal then AST will be checked for further assessment of abnormalities. Alkaline phosphatase and total bilirubin will be obtained if evidence of liver disease present on ALT and/or AST to assess for need of drug interruption	

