10.2. Permanent Discontinuation of Study Drug

Any subject who is permanently discontinued from investigational product for an AE or abnormal laboratory result should have the reason for investigational product discontinuation reported as the AE or abnormal laboratory value.

Patients will discontinue study drug if the following disease related clinical events occur during the study period:

- Unprovoked venous thromboembolism (deep vein thrombosis, pulmonary embolism)
- GCA relapse occurs with objective evidence of severe ischemic event (vision loss, stroke, critical limb ischemia)
- Second GCA relapse occurs during study period

Patients will discontinue study drug following temporary interruption of the study drug if either of the following occurs.

- Study drug has been held due to a study drug-related laboratory abnormality necessitating temporary interruption (Table 3) and the laboratory abnormality that led to the investigational hold has not returned to a level at which the investigational product can be resumed (Table 3) by 4 weeks (28 days) for renal function (as determined by eGFR) or 6 weeks for the remaining laboratory parameters (42 days) from the date investigational hold commenced. For example: Example 1: a patient would be withdrawn from the study if the renal function declined due to study drug (i.e. not intercurrent illness) and the eGFR decreased to 30 mL/min/1.73m² and hold

commenced on January 1st.but the eGFR had not returned to ≥ 50 mL/min/1.73 m² by January 29th. Example 2: a patient would be withdrawn from the study if the WBC count decreased below <2000 cells/ μ L on January 1st and did not return to a value of >2500 cells/ μ L by February 11th.

- If following a study drug interruption for an identified laboratory abnormality (Table 3) the same laboratory parameter that led to study drug interruption is again affected by reinitiation of study drug. For example, platelet count prior to study drug was 150,000/uL but decreases to 50,000/uL while on the study drug. Study drug is held and the platelet count improves to 125,000/uL allowing reinitiation of study drug. Following reinitiation the platelet count decrease again to 50,000/uL.
-

In addition discontinuation of the study drug will occur if any one of the following laboratory abnormalities occur:

- ALT or AST >8 x ULN
- ALT or AST >5 x ULN for more than 2 weeks after temporary interruption of investigational product

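### For a serious, baricitinib-related infection or zoster episode, section 5.6.1 requires withdrawal, Table 3 allows resumption, and section 10.2 does not say which governs

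*Combined protocol and SAP*

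**What the plan says.** Four places in the protocol bear on the same episode.

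- **Section 5.6.1 (under Dose Justification):** if a serious adverse event related to study medication occurs, "the dose will not be decreased rather the study drug will be withdrawn". The rule is mandatory and has two conditions: the event is serious, and it is related to study medication.
- **Section 10.1 and Table 3:** "Investigational product must be held in the following situations and may be resumed as noted in the" table. One row is symptomatic herpes zoster, with resumption once the lesions have scabbed over and are improving. Another is "Severe infection that, in the opinion of the investigator, merits the IP being discontinued", with resumption once the infection has cleared. Section 10.1 introduces interruption as a response to adverse events or "abnormal laboratory values that may have an unclear relationship to investigational product".
- **Section 6.2 (Risk Assessment):** on a clinical diagnosis of zoster, "the investigator will interrupt investigational product, initiate standard of care".
- **Section 10.2 (Permanent Discontinuation):** one list opens with "Patients will discontinue study drug if the following disease related clinical events occur during the study period" and covers unprovoked venous thromboembolism, relapse with a severe ischemic event, and a second relapse. Further lists give laboratory criteria, pregnancy and malignancy. A closing list of possible reasons allows stopping for medical or safety reasons or by investigator decision. No item names a drug-related serious adverse event.

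Section 12.4 defines seriousness by outcome, for example death, threat to life or hospitalization.

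**The concern.** An infection that puts a subject in hospital and is attributed to baricitinib meets both conditions of section 5.6.1. It may also meet the severe-infection row of Table 3. One passage ends treatment; the other permits a restart. Staff who turn to section 10, where the stopping criteria are kept, would not find the section 5.6.1 rule there and could restart the drug in good faith against it.

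The scenario is foreseeable. Section 6.2 reports infections as the commonest treatment-emergent event with baricitinib, and subjects also start on 10, 20 or 30 mg/day of prednisone (Table 1). The primary objective is safety and tolerability, and section 11 counts adverse events related to study drug. Relatedness will therefore be judged for such events, and the section 5.6.1 trigger will come into play.

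**Working it through.** The plan gives no figure to reproduce, so the check compares the passages.

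**Step 1. Where do the rules overlap?**

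| Infection or zoster episode | Section 5.6.1 | Table 3 | Conflict? |
|---|---|---|---|
| Serious (12.4) and judged related | Withdraw | Hold, may resume | Yes |
| Not serious, related or not | Not triggered | Hold, may resume | No |
| Serious, judged unrelated or of unclear relationship | Not triggered | Hold, may resume | No |

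Only the first row conflicts. Severity and seriousness are separate scales (sections 12.5 and 12.4), so an infection in the severe-infection row is not automatically a serious adverse event. Symptomatic zoster need not be one either.

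**Step 2. Could *withdrawn* in section 5.6.1 mean a temporary hold?** Probably not. Section 5.2 provides the 12-week safety visit for all "subjects, including those with earlier study drug withdrawal", which uses the word for ending the drug early. Terminology alone does not settle it, though. The severe-infection row says *discontinued* inside a table of temporary interruptions, and section 12.8 speaks of discontinuation that may be temporary or permanent.

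**Step 3. Does the *unclear relationship* wording in section 10.1 separate the rules?** Only in part.

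- The ALT/AST row permits resumption only if baricitinib is judged not to have caused the rise. A relatedness condition was therefore written for that row, but for neither the infection nor the zoster row.
- Section 10.2 applies the Table 3 hold-and-resume scheme to laboratory abnormalities attributed to study drug. Table 3 as a whole is therefore not confined to events of unclear cause.

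**Step 4. Does section 10.2 settle it?** No. Its named criteria omit the drug-related serious event, and the general reasons at the end are discretionary, whereas section 5.6.1 is mandatory.

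**Step 5. Size.** The planned sample is 15 (section 13). One subject handled one way rather than the other moves the proportion discontinued by 1/15 = 0.067, or 6.7 percentage points. The documents give no rate of serious, drug-related infection at this dose in this population, so the chance of the situation arising is not estimated.

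**The case against.** The strongest reply is that the two passages can both be obeyed. Table 3 makes the hold compulsory but resumption optional, so an investigator who holds the drug and never restarts it complies with both. Section 5.6.1 is a dose-justification paragraph whose main point is that the dose is never reduced; operating rules belong in section 10, which gives the investigator discretion to stop. This is one site, and section 12.2 has every adverse event reported to the principal investigator, which limits inconsistent handling. The triggering event is counted in the primary endpoint either way.

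Much of this stands. A reader might infer that any infection or zoster episode in Table 3 carries two opposite instructions. The documents do not support that: the overlap is confined to serious, related episodes, and optional resumption is not the opposite of withdrawal. A reader might also treat the proportion discontinued as the trial's tolerability endpoint. Section 11 does not list it, and section 14 plans only descriptive tabulation. Nor can a probability of occurrence be attached, because any event rate would be unsourced. Such a figure would also give the chance of the event, not the chance that it is handled differently, which further requires recovery and a decision to restart.

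What the reply does not remove is that Table 3 permits a restart that section 5.6.1 forbids, with no statement of precedence.

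**Conclusion.** The inconsistency is real and narrow. It is a matter of unstated precedence between passages, and it does not call the statistical design into question. Its effects are on re-exposure after a related serious event and on the count of subjects discontinued. The related serious event itself is reported under either reading, and the calculations in section 13 are untouched.

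The conclusion rests on reading *withdrawn* as permanent, which section 5.2 supports, and on the absence of any seriousness or relatedness exception in the two infection rows. The per-subject figure assumes 15 treated subjects. Section 10.2 allows replacement of subjects withdrawn from the study while enrollment is open, and section 14 summarizes all treated subjects, so replacements would enlarge the denominator and make each case slightly smaller.

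**What to change.** Reconcile sections 5.6.1, 6.2, 10.1 with Table 3, and 10.2. State in section 10.2 the single rule that applies when an infection or zoster episode is both serious and judged related to study drug, and cross-refer to it from the other three places. Clarify the word *discontinued* in the severe-infection row so that it fits a table of temporary interruptions. Which rule applies is a clinical decision for the sponsor, and this review takes no position on it.

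The cost is a short protocol amendment. Sample size, endpoints and planned analyses stay as they are, and there is no statistical downside.

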5.6.2. Justification of Trial Dose

Baricitinib doses of 1 mg, 2mg, 4 mg, and 8 mg have been investigated in subjects with rheumatoid arthritis. Doses ≤ 4 mg have shown efficacy in rheumatoid arthritis with adverse event rates similar to placebo. However, adverse event rates have been noticed to be higher in subject groups receiving 8 mg [32-34, 39].

5.6.3. Glucocorticoids (prednisone)

Glucocorticoids are considered by consensus expert opinion to be the only class of medications that has shown consistent efficacy in GCA and are considered standard of care. As such all subjects will receive background prednisone at time of enrollment and then undergo standardized taper.

5.6.4. Justification of Glucocorticoid Taper

Consensus guidelines recommend an increase in glucocorticoid treatment at the time of relapse to a previous higher dose, followed by repeat attempts at tapering once symptoms have improved/stabilized [40]. The protocol standardized tapering regimen is expedited compared to clinical practice in order to assess preliminary efficacy of the study drug.

Study subjects may enter the standardized taper at one of three levels; 30 mg, 20 mg or 10 mg. These strata were specifically designed to allow for appropriate increase of GC in response to the relapsing disease in a manner proportional to the dose of GC the subject was on at the time of relapse. It is common practice in treating relapses to increase GC to a prior dose in which the subject was asymptomatic. As such the three tier strata allows for clinicians to increase GC appropriately to achieve symptomatic control prior to a standardized taper instead of mandating

an increase to a required entry dose regardless of the GC dose at time of relapse. For example, it would be considered unnecessary, in the majority of circumstances, to increase a patient from 5 mg/day of prednisone to 30 mg/day for a moderate relapse of PMR symptoms, however an increase to 10 mg/day would be reasonable.

